13.5 Analysis of Primary Endpoints

Primary Endpoint: The primary endpoint of the study is global progression-free survival in patients with melanoma brain metastases who are treated with troriluzole/ipilimumab/nivolumab (INT) vs. ipilimumab/nivolumab (INP).

Analysis of the primary endpoint will be based on the proportional hazards mixture cure model (PHMC) with treatment (INT/INP) as the only predictor. Modeling of parameter estimates of survival and cure will be semiparametric with bootstrapped standard errors and stratified by the randomization factors. Analyses will be conducted using the *smcure* package from R, the PSPMCM macro from SAS, or any modification to these packages available at the time of analysis. Inference will be based on Z-values and associated p-values. Cure proportions will be based on estimation from the incidence portion of the model and metrics of PFS from patients who are not cured will be based on the latency portion of the model. Comparisons of cure rates will be expressed as odds ratios with confidence intervals, and comparisons of PFS will be expressed as hazard ratios with confidence intervals. The distributions of events for INT and INP will be summarized using marginal survival function curves. Point estimates at 6 months will be presented with confidence intervals.

13.6 Analysis of Secondary Endpoints

Overall Survival

Overall Survival (OS) is defined as the time from randomization (or registration) to death due to

any cause, or censored at date last known alive. Estimates of overall survival will also be from a PHMC model (Section 13.5). Long-term survival estimates and comparisons will be based on the incidence portion of the model; hazards of death will be based on the latency portion of the model. The distribution of deaths will be summarized using marginal survival function curves.

Intracranial or Extracranial Response

The proportion of patients in each treatment arm with intracranial response (RECIST) will be presented with exact, 90% binomial confidence intervals. The randomized treatment arms will be compared using Fisher's exact test. Comparable comparisons will be conducted for extracranial response (RECIST).

Intracranial or Extracranial PFS

Extracranial PFS is defined as the time from first dose of study therapy to documented extracranial progression (per RECIST) or death, whichever occurs first. Intracranial PFS is defined as the time from first dose of study therapy to documented intracranial progression or death, whichever occurs first. For both endpoints, the follow-up of patients who have neither died nor progressed at the time of analysis will be censored at the date of last adequate disease assessment. Treatment comparisons of intracranial or extracranial PFS will be based on PHMC methods outlined in Section 13.5. Point estimates at 6 months will be presented with confidence intervals.

Safety Data

Adverse events will be summarized for all patients having received one or more doses of study therapy and reported according to CTCAE (Version 5.0). The data for each dose cohort in the dose escalation will be summarized separately as will the safety data from the randomized portion of the trial. The proportions of patients in the randomized trial with grade-3 or higher toxicities will be presented with 90% exact binomial confidence intervals. The incidence of events that are new or worsening from the time of first dose of therapy will be summarized according to system organ class and/or preferred term, severity (based on CTCAE grade), type of adverse event, and relation to study treatment. Deaths reportable as SAEs and non-fatal serious adverse events will be listed by patient and tabulated by primary system organ class, and type of adverse event. Of particular interest are serious neurologic events such as seizure, intracranial hemorrhage, and radiation necrosis.

Tolerability

Drug administration will be summarized for all patients having received one or more doses of study therapy. Tolerability will be described by the number of induction cycles administered, the number of maintenance cycles administered, and the frequency of discontinuation of therapy due to toxicity.

Planned Subgroup Analyses

Pre-specified subgroup analyses according to baseline characteristics will be conducted using PHMC methods and will be based on the statistical interaction of treatment assignment and the characteristic. Statistical inference will be based on the interaction p-value. Forest plots will be used to show the results graphically.

Preplanned sub-analyses will be conducted on patients who received on-study brain-directed stereotactic radiation (“radiation salvage subgroup”). Tumor response in the non-irradiated brain lesions and overall survival will be described.

Preplanned sub-analyses will be conducted on patients who required corticosteroids to treat either cerebral edema or immune-related adverse events (“steroid-treated subgroups”).

Due to the potential for guarantee-time bias in these analyses, a conditional landmark approach will be used to evaluate these data.

Exploratory Analyses

Biomarkers of blood and tissue: Analyses of blood and tissue biomarkers will be based on descriptive statistics, as appropriate for the biomarker. To examine response according to pre-treatment levels of biomarkers, the study sample will be divided retrospectively according to response and summarized descriptively for the resulting groups. These will be compared using Wilcoxon rank-sum tests for markers measured on a continuous scale, or Fisher’s exact tests for those measured on a categorical scale. Where appropriate, visualization of the relationship between baseline marker levels and the distributions of PFS or OS will employ marginal survival function estimates stratified by biomarker levels.

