4.3 General Guidelines for Other Investigative Sites

Eligible participants will be entered on study centrally at DF/HCC by the Study Coordinator. All sites should contact the Study Coordinator at DFC to verify slot availability:
[contact]

The required form, the External Site Subject Registration Form, can be found in Appendix E.

Following registration, participants should begin protocol therapy within 10 days. Issues that would cause treatment delays should be discussed with the Sponsor-Investigator. If the subject does not receive protocol therapy following registration, the subject must be taken off study in the CTMS (OnCore) with an appropriate date and reason entered.

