11.5 Progression-Free Survival

Progression-Free Survival: Progression-Free Survival (PFS) is defined as the time from randomization (or registration) to the earlier of progression in the intracranial or extracranial sites or death due to any cause. Herein, the term “PFS” refers to PFS in both the intracranial and extracranial compartments (global). The follow-up of participants alive without disease progression is censored at date of last disease evaluation.

Time to Progression: Time to Progression (TTP) is defined as the time from randomization (or registration) to progression, or censored at date of last disease evaluation for those without progression reported.

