Following the Safety Run-in, all participants will be enrolled on the randomized portion of the study.

Primary Endpoint. The primary endpoint of the study is global progression-free survival in patients with melanoma brain metastases who are treated with INT vs. INP. Of particular interest will be PFS at 6 months.

PFS is defined as the time from random assignment to the earlier of death or documented disease progression in the intracranial or extracranial compartments. The follow-up of patients who have neither died nor progressed will be censored at the date of the last follow-up visit.

Secondary Endpoints. The secondary objectives and their associated endpoints evaluate other important clinical outcomes, including overall survival (OS), intracranial response rate (RR) and

PFS, extracranial RR and PFS, and safety (number of participants experiencing adverse events, particularly neurologic events). We will also investigate:

- tolerability (number of induction cycles administered, number of maintenance cycles administered)
- use of corticosteroids for management of symptomatic cerebral edema (number of participants)
- use of corticosteroids for management of immune related adverse events (number of participants who require prednisone ≥ 1 mg/kg or equivalent)
- frequency of clinically-indicated stereotactic radiation therapy to the brain on study (number of patients, number of instances and number of lesions irradiated)
- frequency of clinically-indicated surgical intervention to the brain on study (number of participants)

Planned subgroup analyses according to baseline characteristics:

- Prior anti-PD-1 exposure (yes vs. no – if yes then adjuvant vs. metastatic setting)
- Prior ipilimumab exposure (yes vs. no)
- Age (<65 years vs 65 years or older)
- ECOG (0 vs 1)
- LDH at baseline (normal vs. elevated)
- Number of brain metastases (<3 vs 3 or more)
- Brain-directed stereotactic radiation therapy prior to study entry (yes vs. no)
- Craniotomy prior to study entry (yes vs. no)

Planned subgroup analyses according to on-study events:

- On-study brain-directed stereotactic radiation therapy (yes vs. no)

Exploratory Endpoints:

- associations between BRAF/NRAS mutation status and response endpoints, as well as tissue biomarker profiles between paired tissues from extracranial and intracranial metastases from individual patients, where available

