13.7 Reporting and Exclusions

Evaluation of Toxicity

All participants will be evaluable for toxicity from the time of their first treatment.

Evaluation of the Primary Efficacy Endpoint

The analysis of the primary endpoint will be conducted using the intention-to-treat principal, meaning all randomized patients will be evaluated according to the treatment assigned at the time of enrollment.

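### Intracranial and extracranial PFS are counted from first dose although the randomized arms are compared on them, while global PFS and OS are counted from randomization (or registration)

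*Combined protocol and SAP*

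**What the plan says.** The primary endpoint is global PFS. Section 13.1 states "PFS is defined as the time from random assignment to the earlier of death or documented disease progression in the intracranial or extracranial compartments". Section 11.5 gives nearly the same origin: "defined as the time from randomization (or registration) to the earlier of progression in the intracranial or extracranial sites or death".

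Section 13.6 handles the secondary time-to-event endpoints in two ways. For survival it says "Overall Survival (OS) is defined as the time from randomization (or registration) to death due to" any cause. For the regional endpoints it says "Extracranial PFS is defined as the time from first dose of study therapy to documented extracranial progression" or death, and "Intracranial PFS is defined as the time from first dose of study therapy to documented intracranial progression or death, whichever occurs first". The same paragraph then sends the treatment comparison of both regional endpoints to the mixture cure model of Section 13.5, which compares INT with INP, and promises six-month point estimates.

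Section 13.7 sets the analysis population for the primary endpoint only: "all randomized patients will be evaluated according to the treatment assigned at the time of enrollment". No population is named for intracranial or extracranial PFS. Sections 4.1 and 4.3 foresee registered participants who never receive protocol therapy and have them taken off study in the trial management system. For external sites, Section 4.3 adds: "Following registration, participants should begin protocol therapy within 10 days". Section 4.1 sets no such limit for the coordinating institutions.

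**The concern.** A comparison of randomized arms is protected by randomization only if follow-up starts there and everyone randomized is in it. A clock that starts at first dose makes entry depend on something that happens after randomization. Three things follow from the wording.

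- A patient randomized but never dosed has no start date for either regional endpoint, yet counts in the primary analysis.
- A patient who dies between randomization and first dose has a global PFS event and no valid regional time.
- The six-month regional estimates are read at a later date than the six-month global estimate.

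Readers of a brain-metastasis trial will set the three six-month figures side by side to see which compartment drives the result. Global PFS is by definition the earlier of progression in either compartment or death, so the same event should not carry two different times.

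**Working it through.** **1. The definitions side by side**

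| Endpoint | Section | Clock starts | Censored at | Population named |
|---|---|---|---|---|
| Global PFS | 13.1 | randomization | last follow-up visit | all randomized (13.7) |
| Global PFS | 11.5 | randomization or registration | last disease evaluation | – |
| OS | 13.6 | randomization or registration | last known alive | none |
| Intracranial PFS | 13.6 | first dose | last adequate assessment | none |
| Extracranial PFS | 13.6 | first dose | last adequate assessment | none |

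The first-dose origin cannot be a rule for the run-in only. The run-in has one arm (Section 1.1), and the paragraph in 13.6 prescribes a treatment comparison.

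**2. Inputs for the size of the effect**

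No figure in the plan depends on the regional origin, so there is none to reproduce. The illustration borrows the global PFS assumptions of Section 13.2: control six-month PFS 0.6 (taken here as the figure for all control patients), cure fractions 0.30 and 0.50, hazard ratio 0.557. The 10-day lag is from Section 4.3, assuming randomization on the day of registration. A month is 30.4375 days, so 10 days is 0.3285 months.

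Control curve: S(t) = 0.3 + 0.7·exp(-λt). Setting S(6) = 0.6 gives exp(-6λ) = 0.3/0.7, so λ = 0.1412 per month.

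INT curve: S(t) = 0.5 + 0.5·exp(-0.557·λ·t), so S(6) = 0.812. The plan states approximately 0.8. Its odds ratio also reproduces: (0.5/0.5)/(0.3/0.7) = 2.33.

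**3. Shift in six-month PFS for a lag m of 10 days**

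- If patients must be event-free at first dose, the regional figure is S(6+m)/S(m). Control: 0.5864/0.9683 = 0.606, a change of +0.6 points. INT: 0.814 against 0.812.
- If six months is simply read 10 days later, it is S(6+m). Control: 0.586, a change of -1.4 points. INT: 0.804 against 0.812.

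The INT minus control difference is 0.8119 - 0.6000 = 0.212 from randomization. It becomes 0.8143 - 0.6056 = 0.209 or 0.8039 - 0.5864 = 0.218, a movement of -0.3 to +0.6 points.

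If the hazard acts from randomization, 1 - 0.9683 = 3.2% of control patients would have their event inside a 10-day lag.

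**4. One event, two times**

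The Day 169 scan falls 168 days after Day 1, and Section 10.1 allows 7 days more. A progression seen on a scan 7 days late after a 10-day lag is timed at 168 + 7 = 175 days for regional PFS and 175 + 10 = 185 days for global PFS. Six months is 6 × 30.4375 = 182.6 days, so the two fall on opposite sides. This happens whenever lag plus scan delay exceeds 182.6 - 168 = 14.6 days.

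**5. Patients without a time zero**

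The documents give no non-start rate. Assuming 0 to 10% of up to 90 randomized patients, 0 to 9 would have no regional time zero and 81 to 90 would.

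**The case against.** The strongest reply is that this is a definitional clean-up in secondary endpoints. They carry no alpha, power statement or stopping rule, and a first-dose clock matches a scan calendar that counts from Day 1. Part II is double-blind, so the lag should not differ systematically by arm. Ten days is a ceiling for external sites, not an expected lag. With about 45 patients per arm, the binomial standard error at 0.60 is sqrt(0.6 × 0.4/45) = 7.3 points, so even -1.4 points is about 0.2 of a standard error. All of this stands.

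Several stronger inferences are tempting, and the documents do not support them.

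- **That the plan excludes untreated patients from the regional analyses.** It states no such exclusion. It names no population, and the gap follows from the clock.
- **That many pre-dose progressions would be mistimed.** No scan is scheduled between baseline and the Day 43 MRI, and Section 5.2 requires eligibility on Day 1. A pre-dose death or an unscheduled scan is the realistic route.
- **That much information is lost with undosed patients.** Taken off study as Sections 4.1 and 4.3 direct, most would be censored near time zero even with a randomization clock. The exception is a death that is captured.
- **That 10 days, as a share of six months, is the size of the error.** 10/183 = 5.5% is a share of time, not a change in PFS.
- **That moving the origin alone makes global PFS the earlier of the regional times.** The censoring rules differ as well.

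What the reply does not remove is the inconsistency. No section explains the different origin or gives an undosed randomized patient a substitute start date.

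**Conclusion.** The point holds as an inconsistency in the secondary endpoints. Intracranial and extracranial PFS are compared between randomized arms on a clock that starts after randomization, against the plan's own practice for global PFS and OS. Undosed randomized patients have no regional time zero, and the three six-month PFS estimates refer to different dates.

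The numerical effect is small: about -1.4 to +0.6 percentage points in control six-month PFS at a full 10-day lag, with no imbalance between arms expected under blinding. This rests on the global PFS curve standing in for the regional ones and on registration and randomization falling on the same day. The 0 to 9 patients rest on an assumed 0 to 10% non-start rate. A reader might infer that the primary result is at risk. It is not: the origin of global PFS, its test, the sample size and the power do not depend on the regional definitions.

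**What to change.** In Section 13.6, define intracranial and extracranial PFS from the date of randomization, in all randomized patients, analysed as assigned. Use registration or first dose as the origin only when describing the single-arm run-in.

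Adopt one censoring rule for global, intracranial and extracranial PFS, for example the last adequate disease assessment, and write it the same way in Sections 11.5, 13.1 and 13.6. Because the Day 43 visit has a brain MRI but no body CT, the rule should say how an assessment of one compartment counts for global PFS. Global PFS is then consistent with the earlier of the two regional times.

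The cost is wording in three sections, best settled before unblinding. Randomization dates are already recorded, so the new origin needs no new data, and sample size and alpha do not change. The censoring edit also touches the primary endpoint, but Sections 11.5 and 13.1 already disagree on that rule and one must be chosen in any case.

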1.3 Secondary Objectives

The secondary objectives are to evaluate other important clinical outcomes, including:

- overall survival
- intracranial response rate (RR) and PFS
- extracranial RR and PFS
- safety (number of participants experiencing adverse events, particularly serious neurologic events such as seizure, MRI-defined intracranial hemorrhage, radiation necrosis)
- tolerability (number of induction cycles administered, number of maintenance cycles administered)
- use of corticosteroids for management of symptomatic cerebral edema (number of participants)
- use of corticosteroids for management of immune related adverse events (number of participants who require prednisone ≥ 1 mg/kg or equivalent)

- frequency of clinically-indicated stereotactic radiation therapy to the brain on study (number of patients, number of instances and number of lesions irradiated)
- frequency of clinically-indicated surgical intervention to the brain on study (number of participants)

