5.8 Criteria for Taking a Participant Off Protocol Therapy

Safety Run-In and Randomized Treatment:

Duration of therapy will depend on individual response, evidence of disease progression and tolerance. In the absence of treatment delays due to adverse event(s), treatment may continue until Day 337 or until one of the following criteria applies:

- Disease progression, with the following exceptions:
 - To allow for the possibility of pseudoprogression, investigators may continue to treat a patient beyond progression until the next assessment if the investigator believes the patient is clinically benefitting (must document in progress note). If PD is confirmed on a subsequent scan, therapy must be discontinued.
 - Investigators may continue to treat a patient beyond progression if the progressing lesion(s) can be addressed with brain-directed SRT (See Section 5.6). *NOTE:* To continue on study after SRT, the subject must have at least 1 non-irradiated target lesion and/or non-target lesion in the brain or body.
- Intercurrent illness that prevents further administration of treatment
- Unacceptable adverse event(s)
- Participant demonstrates an inability or unwillingness to comply with the oral medication regimen and/or documentation requirements
- Participant decides to withdraw from the protocol therapy
- General or specific changes in the participant's condition render the participant unacceptable for further treatment in the judgment of the treating investigator

Participants will be removed from the protocol therapy when any of these criteria apply. The reason for removal from protocol therapy, and the date the participant was removed, must be documented in the case report form (CRF). Alternative care options will be discussed with the participant.

When a participant is removed from protocol therapy and/or is off of the study, the participant's status must be updated in OnCore in accordance with [REGIST-OP-1](#).

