10. STUDY CALENDAR

10.1 Scheduling windows

Baseline evaluations are to be conducted within 1 week prior to start of protocol therapy. Scans and x-rays must be done <4 weeks prior to the start of therapy. If the participant's condition is deteriorating, laboratory evaluations should be repeated within 48 hours prior to initiation of the next cycle of therapy. Assessments must be performed prior to administration of any study agent. Study assessments and agents should be administered within + 7 days of the protocol-specified date for Days 1-309, and within + 14 days of the protocol-specified date for Days 337-673.

	Baseline	Cycles 1-4: Induction				Cycles 5-13			End of Treatment (EOT) Cycle 14	Follow-Up Visit #1	Follow-Up Visits #2-4 ⁱ	Final Follow-Up Visit ^j	EDC Timepoints
		Day 1	Day 22	Day 43	Day 64	Day: 85 169 253	Day: 113 197 281	Day: 141 225 309	Day 337 or sooner	Within 30 days post EOT	Day: 421 505 589	Day 673 or sooner	
Troriluzole or placebo^T (continuous oral twice daily dosing)		T-----T											Medication Diary Documentation Day 43, 85, 169, 253, EOT
Ipilimumab and Nivolumab		I+N	I+N	I+N	I+N								Day 1, 22, 43, 64
Nivolumab						N	N	N	N				Day 85, 113, 141, 169, 197, 225, 253, 281, 309
Informed consent	X												N/A
Demographics	X												Baseline
Medical history, including BRAF mutational status	X												Baseline
Physical exam	X	X	X	X	X	X	X	X	X	X	X	X	Baseline
Vital signs	X	X	X	X	X	X	X	X	X	X	X	X	Baseline
Height	X												Baseline

	Baseline	Cycles 1-4: Induction				Cycles 5-13			End of Treatment (EOT) Cycle 14	Follow-Up Visit #1	Follow-Up Visits #2-4 ⁱ	Final Follow-Up Visit ^j	EDC Timepoints
		Day 1	Day 22	Day 43	Day 64	Day: 85 169 253	Day: 113 197 281	Day: 141 225 309	Day 337 or sooner	Within 30 days post EOT	Day: 421 505 589	Day 673 or sooner	
Weight	x	x	x	x	x								Baseline
Performance status	x	x				x			x	x			Baseline, EOT
CBC w/diff, plts and CMP ^a	x	x	x	x	x	x	x	x	x	x	x	x	N/A
Gamma-glutamyl transferase (GGT), LDH, amylase, lipase, TSH, free T4 ^b	x					x			x	x			GGT only: Baseline, Day 85, 169, 253, 337
B-HCG ^c , pro-BNP, troponin-T	x												N/A
EKG	x					x							Baseline, Day 85, 169, 253. If EKG is performed during any other Cycle, it must be captured in EDC.
MRI Brain (with and without gadolinium contrast) for intra-	x			x		x			x				Baseline, Day 43, 85, 169, 253. If Intracranial Tumor Measurements are performed

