
Study Drug Dose and administration schedule:
 
T: Troriluzole [FC-4157, BHV-4157] or placebo. Safety Run-In cohort will start at 140mg PO Q AM and 280mg PO QPM only open label Troriluzole. This dose level may change based on participant cohort and MTD determined in Safety Run-In (Section 5).
 
I+N: Ipilimumab + nivolumab induction: ipilimumab 3 mg/kg IV Q3 weeks and nivolumab 1 mg/kg IV Q3 weeks.
 
N: Nivolumab: nivolumab 480mg IV Q4 weeks.
 
Footnotes:
 
a: Comprehensive metabolic panel (CMP): Albumin, alkaline phosphatase, total bilirubin, bicarbonate, BUN, calcium, chloride, creatinine, glucose, potassium, total protein, SGOT [AST], SGPT [ALT], sodium.
 
b: TSH with reflex to free T4 is acceptable replacement for TSH and free T4.
 
c: Serum pregnancy test (women of childbearing potential).
 
d: MRI Brain (with and without gadolinium contrast) for intra-cranial tumor measurements with thin cuts. Slice thickness must be 2 mm or less—specify when ordering.
 
e: PET/CT scan is an allowable alternative to CT scan if approved by Sponsor-Investigator. Tumor assessments will be performed as per standard of care during Days 421-589 and will be captured on CRFs.
 
f: Research blood samples. At each time point indicated, 2 green top (heparin) tubes (10 ml each) will be collected for biomarker/correlative studies listed in Section 9.
													

	Baseline	Cycles 1-4: Induction				Cycles 5-13			End of Treatment (EOT) Cycle 14	Follow-Up Visit #1	Follow-Up Visits #2-4 ⁱ	Final Follow-Up Visit ^j	EDC Timepoints
		Day 1	Day 22	Day 43	Day 64	Day: 85 169 253	Day: 113 197 281	Day: 141 225 309	Day 337 or sooner	Within 30 days post EOT	Day: 421 505 589	Day 673 or sooner	

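### Safety in 13.6 is summarized only by crude proportions although observation time depends on progression; add incidence by Day 85 and a time-based summary split there (minor)

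*Combined protocol and SAP*

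**What the plan says.** Section 1.2 puts the safety of adding troriluzole in the primary objective. Section 1.3 defines the measure as a count of participants: "safety (number of participants experiencing adverse events, particularly serious neurologic events such as seizure, MRI-defined intracranial hemorrhage, radiation necrosis". In 13.6 the summary covers everyone who received a dose: "The proportions of patients in the randomized trial with grade-3 or higher toxicities will be presented with 90% exact binomial confidence intervals". Other events go into incidence tables, and the paragraph closes by singling out neurologic events: "Of particular interest are serious neurologic events such as seizure, intracranial hemorrhage, and radiation necrosis". No person-time, time-to-event or fixed-window safety summary is planned. The landmark approach in 13.6 follows the radiation-salvage and steroid-treated sub-analyses and is not stated for the safety tables.

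Observation is governed by these provisions:

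- **Scheduled MRI.** The data-capture column of the Section 10 calendar reads "Baseline, Day 43, 85, 169, 253. If Intracranial Tumor Measurements are performed". The calendar also marks an MRI at End of Treatment, which is Day 337 or sooner, and none at the follow-up visits.
- **End of treatment.** Under 5.8, "treatment may continue until Day 337 or until one of the following criteria applies". Disease progression is the first criterion, with exceptions for possible pseudoprogression and for lesions treated with brain-directed stereotactic radiation (SRT).
- **Adverse event capture.** Section 7.3 sets reporting to 30 days after the last dose. Sections 5.9, 6.1 and 7.6 say that new unrelated events in follow-up are not recorded.
- **After treatment.** "Tumor assessments will be performed as per standard of care during Days 421-589 and will be captured on CRFs". Patients who stop early are seen in person every 84 days until five follow-up visits are complete, and adverse events are evaluated at all visits.

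**The concern.** A patient who progresses at the Day 43 scan counts in the denominator exactly like one scanned to Day 337, but has far less scheduled opportunity for an event to be found. If one arm progresses later, it is observed longer. Its crude proportion can then be higher at the same underlying risk.

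The link is most direct for hemorrhage found only on MRI. The rule on unrelated events in follow-up extends it to other new events, because that rule shortens capture for early stoppers however the event is detected. At stake is whether a modest between-arm imbalance reads as toxicity or as longer observation. Crude proportions alone cannot tell these apart.

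**Working it through.** **Inputs from 13.2.** INP six-month PFS is 0.6, cure fractions are 0.30 (INP) and 0.50 (INT), the hazard ratio is 0.557, and up to 90 patients are randomized (45 per arm). Scan days are from Section 10, taken as 42, 84, 168, 252 and 336 days after the first dose. One month is 30.4375 days. Event hazards are assumptions, as the documents give none. They also state no figure for safety observation time, so there is none to reproduce.

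**Check of the 13.2 inputs.** PFS is S(t) = c + (1 − c)·exp(−λt), with c the cure fraction.

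- INP: λ = −ln(0.3/0.7)/6 = 0.1412 per month.
- INT: λ = 0.557 × 0.1412 = 0.0787 per month, so S(6) = 0.812. The plan says about 0.8.
- Odds ratio: (0.5/0.5)/(0.3/0.7) = 2.33, as stated.

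**MRI-covered time.** Progression is taken as found at the next scheduled scan. Mean time is the sum over scan intervals of interval length × S(interval start).

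- INP: (42 + 42×0.8761 + 84×0.7741 + 84×0.6211 + 84×0.5174)/30.4375 = 7.87 months.
- INT: (42 + 42×0.9486 + 84×0.9024 + 84×0.8239 + 84×0.7607)/30.4375 = 9.55 months.
- Ratio: 1.21.

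Section 2.5 cites toxicity discontinuation of 27% and 36% in earlier studies. Adding either as an exponential stop in both arms gives 6.9 vs 8.3 months (1.20) or 6.5 vs 7.8 months (about 1.2). If observation stops exactly at progression, mean time is c·T + (1 − c)(1 − exp(−λT))/λ with T = 11.04 months. That is 7.23 vs 9.21 months, ratio 1.27.

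**Crude proportions with an equal, constant hazard h.** P = sum over intervals from a to b of S(a)·[exp(−ha) − exp(−hb)].

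| h per month | INP | INT | Ratio | Patients per 45 |
|---|---|---|---|---|
| 0.01 | 7.5% | 9.1% | 1.21 | 0.7 |
| 0.02 | 14.3% | 17.2% | 1.20 | 1.3 |

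With exact progression times, 0.01 gives 6.9% vs 8.8% (0.8 patients) and 0.02 gives 13.2% vs 16.6% (1.6 patients).

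**Equal hazards weighted to the first 84 days.** This uses the scheduled-scan model. The overall rate is events divided by MRI-covered time at risk.

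| Hazard to Day 84, then after | Crude ratio INT:INP | Overall rate ratio INT:INP |
|---|---|---|
| 0.02, 0.02 | 1.20 | 1.00 |
| 0.04, 0.01 | 1.12 | 0.93 |
| 0.05, 0.005 | 1.08 | 0.89 |
| 0.05, 0 | 1.04 | 0.86 |

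With exact progression times, the crude ratios in the last three rows become 1.17, 1.12 and 1.08.

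The true ratio is 1.00 in every row. As events move earlier, the crude ratio approaches 1. The overall rate ratio falls below 1, because INT contributes more late, low-risk months.

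**Observation up to Day 85.** The ratio of observed time is (42 + 42×0.9486)/(42 + 42×0.8761) = 81.8/78.8 = 1.04, or 1.08 with exact progression times. Within each period of a split at Day 85, an equal hazard gives a rate ratio of 1.00 in all four rows.

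**The case against.** The strongest objection is to the constant hazard. Section 5.5 treats Days 1-84 as the period of most toxicity, and 6.6 says immune-related events commonly begin within 3 to 10 weeks. On that pattern most of the excess disappears. This stands.

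Observation also does not stop completely. Follow-up visits include adverse event evaluation, standard-of-care imaging is captured over Days 421-589, 11.1 allows extra scans, and 5.8 allows that "Investigators may continue to treat a patient beyond progression if the progressing lesion(s) can be addressed with brain-directed SRT". This stands as dilution. It does not remove the point, because no MRI is scheduled after End of Treatment and new unrelated events in follow-up are not recorded.

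The MRI mechanism does not fit every named event. Seizure is found clinically. Radiation necrosis requires radiation, and SRT on study is permitted for intracranial progression (5.6), so the arm with more progression could have more necrosis. This also stands.

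Finally, the artefact is small. An exact 90% interval for 7 of 45 runs from 7.5% to 27.2%. Section 13.6 plans no between-arm safety test, and the neurotoxicity rule in 13.4 counts events among the first 45 treated patients rather than by arm. No planned decision depends on this.

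A reader might infer that INT will look about 20% less safe, or that a rate per patient-month should replace the crude proportions. The documents support neither. The first needs both the full 13.2 effect and a constant hazard. The second would make INT look safer than it is when toxicity is early.

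**Conclusion.** The concern holds in a limited form. The safety summaries take no account of observation time, and that time depends on the efficacy outcome. If the 13.2 effect is real, MRI-covered time is about 1.2 times longer on INT, and up to about 1.27 times with exact progression times. At an equal constant hazard of 0.01 to 0.02 per month (assumed), MRI-detected events such as asymptomatic hemorrhage would differ about 1.2-fold in crude proportion, roughly 1 patient per 45. With events concentrated early, and progression found at scheduled scans, the ratio is about 1.04 to 1.12. For radiation necrosis the direction is uncertain. If the arms do not differ in progression, this bias is absent. Priority is minor and optional.

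**What to change.** In 13.6, keep the crude proportions with exact 90% intervals. For intracranial hemorrhage, seizure, radiation necrosis and grade 3 or higher events, add by arm:

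1. Incidence by Day 85, when the arms have been observed almost equally.
2. As a supportive summary, time at risk with either cumulative incidence or event rates given separately for the period up to and including Day 85 and the period after it. State where time at risk ends. For MRI-detected events this could be the first event or last brain MRI; for other events, the first event or 30 days after the last dose.

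Do not use one overall rate per patient-month as the main summary.

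The cost is SAP wording and one small table from dates already collected, with no change to visits, procedures or sample size. The downside is wide intervals, especially after Day 85. Stopping at progression may also be informative for intracranial events, so the later-period figures should be read as descriptive.
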